### 5.5 Rescue Medication and Risk Management Plans

Cautions from the manufacturer of Ifenprodil include monitoring for hypotension, palpitations/increased heart rate, and risk of bleeding (including those patients on drugs with a risk of bleeding). Investigators should monitor their patients for occurrence of these adverse events and proceed as follows:

Vasopressin can be used as a rescue therapy for patients who suffer vasodilative shock. If low blood pressure occurs, use of vasopressor medication may also be considered. This may or may be coincident with an increased heart rate, in which case a vasopressor may correct both events. In the event of an increased heart rate in the absence of coincident hypotension, use of a positive inotropic agent may be considered. In the event of an increased risk of bleeding, antifibrinolytic therapy may be considered. Please consult with the Medical Monitor regarding the best course of treatment should any of these events occur.

In addition, patients should be monitored for elevation in liver enzymes. Those patients whose ALT/AST rise to  $>5x$  the upper limit of normal and/or Child Pugh score of 10-15 should be discontinued from study medication (ifenprodil). In addition, the Medical Monitor and DSMB will monitor for the occurrence of these adverse events as part of their normal safety review. Additional guidance or updates to the protocol will be provided if necessary.

The DSMB will review the adverse events profile after 25, 50, 75 and 100 patients enrolled in the study, then every 50 patients thereafter. Particular attention will also be paid to patients over 65 for the frequency and severity of serious adverse events (e.g. ALT/AST, creatinine) as the manufacturer has mentioned caution should be taken in this particular age group. If, based on the DSMB's opinion, there is a significant concern in any of the identified risk groups, additional restrictions may be added to the inclusion/exclusion criteria.

### 5.6 Appropriate Methods of Contraception for Study

Females of childbearing potential: Women who are sexually active with a non-sterilized male partner must use at least 1 highly effective method of contraception, such as oral contraceptives, intrauterine

device, or diaphragm plus spermicide from the time of screening and must agree to continue using such precautions for 90 days after the final dose of study drug(s)

Non-sterilized males: Men who are sexually active with a female partner of childbearing potential must use condom plus spermicide from day 1 through 90 days after receipt of the last dose of study drug(s)

## 6. STUDY TREATMENT

### 6.1 Description of the Investigational Product

The chemical name of Ifenprodil tartrate is (1RS,2SR)-4-[2-(4-Benzylpiperidin-1-yl)-1-hydroxypropyl] phenol hemi-(2R,3R)-tartrate. The drug is more commonly referred to as ifenprodil. Ifenprodil will be provided as white, round, biconvex, film-coated tablets containing 20 mg of the active ingredient. All IP is provided by the sponsor and is produced and handled according to the principles of Good Manufacturing Practice (GMP).

### 6.2 Treatment Administration and Schedule

Tablet/s (20 mg TID arm = 1 tablet; 40 mg TID arm = 2 tablets) will be taken by mouth TID after food (if possible) in the in the morning (AM, upon rising), in the afternoon (PM, 6-10 hours following first dose), and evening (PM, 6-10 hours before the next day's anticipated first dose). Best efforts should be made to keep the three doses approximately 8 hours apart. The length of dosing for the study is up to 2 weeks (either to hospital discharge, or Day 14, whichever comes first).

The first dose of study medication will be taken on day 1 at the first visit, following randomization.

In cases where the patient is unable to swallow tablets the use of a nasogastric/stomach tube is permitted. Crushing and administration of tablets should follow local practices/SOPs.

Study drug administration should continue until the end of Day 14, or hospital discharge, whichever comes first.

### 6.3 Packaging and Labelling

The contents of the label will be in accordance with all applicable regulatory requirements.

**Description of Product:** White, round, biconvex, film-coated tablets containing 20 mg of the active ingredient.

**Investigational Drug Packaging and Labeling:** The study drug (Ifenprodil) will be supplied by Algernon Pharmaceuticals, in cartons containing blister packs (50 tablets contained in 5 blister packs (10 tablets per blister pack)).

The study drug will be provided to the sites by Algernon Pharmaceuticals. Separate labels, as per the GMP regulations and requirements will also be provided for site staff to apply to the packages and blister packs, as provided by the local laws. All investigational labels for the study drug will meet applicable country specific regulatory requirements.

**Storage:** Store in a dry dark place at temperatures no higher than 25°C, keep protected from moisture.

**Dispensing:** Study treatment must be stored in a secure area under the appropriate physical conditions for the product. Access to and administration of the study treatment will be limited to the investigator and authorized site staff.

**Drug Return/Destruction:** The clinical site, upon confirmation with Sponsor, should follow their local regulations for final disposition of unused study treatment.

### 6.4 Accountability

Only patients enrolled in the study may receive study treatment.

The investigator, institution, or the head of the medical institution (where applicable) is responsible for study treatment accountability, reconciliation, and record maintenance (i.e. receipt, reconciliation and final disposition records). Study treatment must be stored in a secure area under the appropriate physical conditions for the product. Access to and administration of the study treatment will be limited to the investigator and authorized site staff.

Under normal conditions of handling and administration, study treatment is not expected to pose significant safety risks to site staff.

The Sponsor (or designee) will review with the Investigator and relevant site personnel the process for IP return, disposal, and/or destruction, including responsibilities for the site versus the Sponsor (or designee). Further details can be found in the Pharmacy Manual.

### **6.5 Compliance with Study Treatment Administration**

Study personnel will review the instructions printed on the package with the study patients prior to dispensing the IP. The IP will be dispensed as noted in [Table 3](#).

## **7. STUDY ASSESSMENTS AND PROCEDURES**

### **7.1 Informed Consent**

Voluntary written informed consent must be obtained before any study-related procedures are performed in accordance with the International Conference on Harmonization (ICH) E6 Guidelines for Good Clinical Practice (GCP) and the regulatory requirements of informed consent for each jurisdiction (e.g. US Title 21 Code of Federal Regulations (CFR) Part 50, Canadian Food and Drug Regulations, Part C Division 5). Consent must be documented by the use of a written consent form approved by Algernon Pharmaceuticals and the IEC/IRB. A copy of the signed informed consent will be provided to the patient/parent/guardian/legal representative signing the form and the original retained in the source documents of the study participant. Documentation of the consent process must be collected with the source documents at the site.

### **7.2 Trial Flowchart**

The trial includes a Screening/Baseline visit, a 2-week open label Treatment Period, and a 6-week Safety Follow-up Period to Day 60. All periods are associated with evaluations and procedures that must be performed at specific time points, as described in [Section 7.3](#). The Schedule of Events ([Table 3](#)) summarises the frequency and timing of trial events.

**Table 3 Schedule of Events**

Trial Activity	Screening/Baseline/ Enrolment visit	Daily until hospital discharge	End of treatment	Follow-up period	
Day	1	2-14	15	29	60
Allowed window for visit (±)	-1 a		2	2	3
Visit	1		2 b	3	4
Informed consent	•				
Inclusion/exclusion criteria including confirmation of COVID-19 diagnosis	•				
Confirmation SARS-CoV-2 h	•	•	•	•	
Pregnancy test	•				
Demographics/Medical History	•				
Physical Exam	•				
Vital signs c	•	•	•	•	
Clinical support data collection f	•	•	•	•	
Safety Laboratory Testing d	•	•	•	•	
Cytokine Markers k	•	•	•		
Child-Pugh Score i	•	•			
PaO 2 and PaO 2 /FiO 2 ratio j	•	•	•	•	
ECG	•				
Cough Severity (VAS) e	•	•	•	•	
Extent of Dyspnea (Likert Scale) e	•	•	•	•	
Adverse Events documented	•	•	•	•	•
Concomitant Medications	•	•	•	•	
Randomization	•				
Administer IP	•	•			
Vital Status					• g

a Screening/baseline may occur up to 24 hours prior to randomization

b Treatment can be given up to 14 days post randomization, or until hospital discharge, whichever comes first. If patient is discharged prior to Day 14, the next visit should be Visit 2.

c Includes blood pressure (measured after the patient has been in a seated position (if possible) for ≥3 minutes of rest), pulse, respiratory rate, body temperature, and SpO2. Body weight and height will be measured at the screening visit only.

d Baseline, Days 3, 5, 8, 11 if hospitalized, Day 15, Day 29

e Baseline, Days 2, 4, 8, and 14 if hospitalized, Day 15 (if not done Day 14), Day 29

f Includes NEW Score, on Baseline, Days 3, 5, 8, 11 if hospitalized, Day 15, Day 29

g Vital status (is patient alive)

h Baseline, Days 5 (or discharge, whichever comes first) and 15. Day 29 for subjects with viral RNA detected at Day 15.

Qualitative (mandatory) and Quantitative (if available) testing done all days.

i Baseline, Days 3, 5, 8, 11 if hospitalized

j Minimum complete baseline, Days 3, 5, 8, 11, 15 and 29. If PaO2 not able to be taken, SpO2 should be obtained using a forehead sensor. Fingertip probes may be used if forehead sensors are not available. Remain consistent with the method of testing for the patient over the course of the study.

k Cytokine markers at Baseline, Day 5, Day 15 (if available per local lab): IFN- $\gamma$ , GM-CSF, IL-6, IL-12, TNF- $\alpha$

## 7.3 Visits

### 7.3.1 Visit 1 (Screening/Baseline/Enrollment)

At Visit 1, information will be collected for evaluation of trial eligibility by provided information as follows and patients will be randomized and dosed after confirmation of eligibility:

- Signing ICF (prior to any trial-related activities)
- Inclusion criteria and exclusion criteria
- Demographics (gender, date of birth, race and ethnic origin) and relevant medical and surgical history
- Confirmation of COVID-19 diagnosis (SARS-CoV-2 RNA confirmation). Include dates of onset of symptoms (if available) and initiation of treatment.
- Pregnancy test (females of reproductive age; Romania: Serum beta-human chorionic gonadotropin [ $\beta$ -HCG]; Rest of World: Serum beta-human chorionic gonadotropin [ $\beta$ -HCG] or urine test is acceptable)
- Vital signs measurements (including pulse, respiration rate, body temperature, systolic and diastolic blood pressure measured with the patient in a seated position [if possible] after  $\geq 3$  minutes of rest), and SpO2. Body weight and height will be included for the screening visit only
- Limited Physical Exam
- Assess baseline measures of clinical support
  - Hospitalized
  - Oxygen requirement
  - Non-invasive mechanical ventilation (via mask)
  - Mechanical ventilator requirement (via endotracheal tube or tracheostomy tube)
  - ECMO requirement
  - Ordinal Scale Assessment
    1. Not hospitalized, no limitations on activities
    2. Not hospitalized, limitation on activities
    3. Hospitalized, not requiring supplemental oxygen
    4. Hospitalized, requiring supplemental oxygen
    5. Hospitalized, on non-invasive ventilation or high flow oxygen devices
    6. Hospitalized, on invasive mechanical ventilation or ECMO
    7. Death
  - For the purposes of eligibility/baseline the worse score from the previous day (Day -1) will be used
  - NEW Score
- Safety laboratory testing
- Child-Pugh Score
- Cytokine Markers
- PaO2 and PaO2/FiO2 ratio
- ECG
- VAS (if possible)
- Extent of Dyspnea (if possible). For the first questionnaire (at baseline), the patient compares their current shortness of breath to their shortness of breath when they are well.)
- Concomitant medications documented
- Randomization\* after eligibility confirmation. All screening/baseline procedures must be completed prior to randomization and administration of study medication.

- Begin administration of study medication after randomization (within 24 hours of screening procedures).

\*Randomization should occur within 24 hours of screening procedures.

### 7.3.2 Daily Assessments (Days 2 - 14; Treatment Period)

At each study day while hospitalized, the following data will be collected:

- Vital signs (including pulse, respirations rate, body temperature, systolic and diastolic blood pressure, SpO2)
- Assess measures of clinical support
  - Hospitalized
  - Oxygen requirement
  - Non-invasive mechanical ventilation (via mask)
  - Mechanical ventilator requirement (via endotracheal tube or tracheostomy tube)
  - ECMO requirement
  - Ordinal Scale Assessment
  - The ordinal scale is an assessment of the clinical status at the first assessment of a given study day. Each day, the worse score for the previous day will be recorded. i.e. on Day 3, Day 2 score is obtained and recorded as Day 2. The scale is as follows:
    1. Not hospitalized, no limitations on activities
    2. Not hospitalized, limitation on activities
    3. Hospitalized, not requiring supplemental oxygen
    4. Hospitalized, requiring supplemental oxygen
    5. Hospitalized, on non-invasive ventilation or high flow oxygen devices
    6. Hospitalized, on invasive mechanical ventilation or ECMO
    7. Death
  - NEW Score (Days 3, 5, 8, 11 if still hospitalized)
- SARS-CoV-2 RNA status testing (Day 5, or discharge, whichever comes first)
- Safety laboratory testing (Days 3, 5, 8, 11 if still hospitalized)
- Child-Pugh Score (Days 3, 5, 8, 11 if still hospitalized)
- Cytokine Markers (Day 5)
- PaO2 and PaO2/FiO2 ratio
- VAS score questionnaire (Days 2, 4, 8, and 14 if still hospitalized)
- Extent of Dyspnea (Likert Scale, Days 2, 4, 8, and 14 if still hospitalized)
- Adverse Events recorded
- Concomitant medications
- IP administration (daily until discharge or Day 14)

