##### Secondary objectives:

- To investigate the clinical efficacy of NP-120 (20 and 40 mg TID) as compared to the control arm as assessed by:
  - Ordinal scale:
    - Time to an improvement of one category from baseline on an ordinal scale.
    - Subject clinical status on an ordinal scale at days 3, 5, 8, 11, and 29.
    - Mean change in the ranking on an ordinal scale from baseline to days 3, 5, 8, 11, 15 and 29 from baseline.
  - National Early Warning Score (NEWS):
    - The time to discharge or to a NEWS of  $\leq 2$  and maintained for 24 hours, whichever occurs first.
    - Change from baseline to days 3, 5, 8, 11, 15, and 29 in NEWS.
  - Oxygenation:
    - Oxygenation free days in the first 28 days (to day 29).
    - Effect on the rate of change of partial pressure of oxygen (PaO2) and PaO2/FiO2 ratio taken at baseline and measured once daily up to 2 weeks of treatment in IP versus control group patients
  - Mechanical Ventilation:
    - Ventilator free days in the first 28 days (to day 29).
    - Incidence and duration of new mechanical ventilation use during the trial.
  - Hospitalization
    - Duration of hospitalization (days).
    - Time to discharge (days)
  - Mortality
    - 15-day mortality.
    - 28-day mortality.

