#### 7.4.5 National Early Warning Score (NEWS)

The NEW score has demonstrated an ability to discriminate patients at risk of poor outcomes ([WHO R&D Blueprint Master Protocol](#); [Royal College of Physicians 2012](#) and [2017](#)). This score is based on 7 clinical parameters. The NEW Score is being used as an efficacy measure.

This should be evaluated at the first assessment of a given study day. These parameters can be obtained from the hospital chart using the last measurement prior to the time of assessment. This is recorded for the day obtained. i.e. on Day 3, Day 3 score is obtained and recorded as Day 3.

A copy of the Table for determining NEW Score can be found in [Appendix 16.1](#).

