## 16. APPENDICES

### 16.1 National Early Warning (NEW) Score

([WHO Blueprint Master Protocol](#); [Royal College of Physicians 2012](#))

PHYSIOLOGICAL PARAMETERS	3	2	1	0	1	2	3
Respiration Rate (per minute)	≤8		9 - 11	12 - 20		21 - 24	≥25
Oxygen Saturations (%)	≤91	92 - 93	94 - 95	≥96			
Any Supplemental Oxygen		Yes		No			
Temperature (°C)	≤35.0		35.1 – 36.0	36.1 – 38.0	38.1 – 39.0	≥39.1	
Systolic BP (mmHg)	≤90	91 - 100	101 - 110	111 - 219			≥220
Heart Rate (per minute)	≤40		41 - 50	51 - 90	91 - 110	111 - 130	≥131
Level of Consciousness				A			V, P, or U

Level of consciousness = alert (A), and arousable only to voice (V) or pain (P), and unresponsive (U).

The aggregate results from all 7 physiological parameters are used to obtain the NEW Score.

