11.5 Secondary Efficacy Analysis: NEWS

11.5.1 Time to the earlier of discharge or NEWS of ≤ 2 maintained for 24 hours

The time to earlier of discharge or NEWS of ≤ 2 maintained for 24 hours (Days) is defined as:

Date of First earlier of discharge or NEWS of ≤ 2 maintained for 24 hours – Date of Baseline Assessment + 1.

If the patient did not experience discharge or NEWS of ≤ 2 maintained for 24 hours, the patient will be censored at the last known date the patient is known to not have experienced either of these events:

Final Date of Confirmation of no discharge nor NEWS of ≤ 2 maintained for 24 hours - Date of Baseline Assessment + 1.

If a patient died before discharge or NEWS of ≤ 2 maintained for 24 hours, the patient will be censored as a competing risk based on the following:

Date of Death - Date of Baseline Assessment + 1.

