12.4 Vital Signs

The following vital signs measurements will be taken at the time points specified in the study procedure schedule (section [Table 1](#)):

- Systolic blood pressure (SBP) (mmHg)
- Diastolic blood pressure (DBP) (mmHg)
- Pulse Rate (beats/min)
- Respiratory rate (breaths/min)
- Body Temperature ($^{\circ}$ C)
- Oxygen Saturation SpO₂ (%)
- Level of Consciousness (Alert, Arousable only to voice, Arousable only to pain, Unresponsive)
- Presence of clinically significant result

Summary statistics for vital sign parameters in accordance to [section 3.1](#) will be presented for baseline and for each scheduled pre and post-baseline visit (which also includes change from baseline, clinical significance) where applicable. These summary tables will be done for Safety population for treatment groups defined in [section 3.4](#).

The listing of vital sign parameters will include all the information collected. In addition, the observations that are used as the baseline record (value) for each parameter will be flagged, and the change from baseline values at each pre and post baseline (scheduled and unscheduled) visit will be presented along with whether the result was clinically significant (AE/MH numbers if applicable) and reasons not done. This listing will be presented by treatment arm (grouping provided in [section 3.4](#)) sorted by patient ID and visit for the Safety population, along with the age and sex and baseline weight of the patient.

12.5 12-Lead Electrocardiogram (ECG)

The following ECG measurements will be taken at the time points specified in the study procedure schedule (section [Table 1](#)):

- Ventricular HR (beats/min)
- PR interval (msec)
- QRS interval (msec)
- ST segment (msec)
- QTcF interval (msec)
- Presence of clinically significant result (normal, abnormal not clinically significant, abnormal and clinically significant)

Summary statistics for 12-Lead ECG parameters in accordance to [section 3.1](#) will be presented for baseline and for each scheduled pre and post-baseline visit (which also includes change from baseline). These summary tables will be done for Safety population for treatment groups defined in [section 3.4](#)

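### The scheduled NEWS scores cannot confirm the 24-hour condition in the secondary measure of time to discharge or low NEWS, and they date it coarsely

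*Protocol*

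**What the plan says.** **The measure.** The protocol's secondary objectives (3.1) include the time to discharge or to a NEWS of 2 or less "maintained for 24 hours, whichever occurs first". SAP 11.5.1 turns this into a time-to-event variable whose event date is the "Date of First earlier of discharge or NEWS of ≤ 2 maintained for 24 hours". Patients without an event are censored at the "Final Date of Confirmation of no discharge nor NEWS of ≤ 2 maintained for 24 hours". Death is a competing risk.

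**The scoring schedule.** The treatment-period list in Protocol 7.3.2 has "NEW Score (Days 3, 5, 8, 11 if still hospitalized". The footnote to Protocol Table 3, repeated in SAP Table 1, gives the whole schedule: "Includes NEW Score, on Baseline, Days 3, 5, 8, 11 if hospitalized, Day 15, Day 29". There is one score on each of those days, since Protocol 7.4.5 says of the score: "This should be evaluated at the first assessment of a given study day".

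**The ingredients.** Protocol Appendix 16.1 says: "The aggregate results from all 7 physiological parameters are used to obtain the NEW Score". Protocol 7.3.2 collects pulse, respiration rate, temperature, blood pressure, SpO2 and oxygen requirement on every hospital day from Day 2 to Day 14. SAP 12.4 adds "Level of Consciousness (Alert, Arousable only to voice, Arousable only to pain, Unresponsive" to the vital signs taken at the SAP Table 1 time points.

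Neither document asks for a repeat score, plans a daily derived score, or says how the 24-hour condition is to be judged. SAP 3.3 does not impute missing values unless stated otherwise, and nothing is stated for this measure.

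**The concern.** The event requires a score of 2 or less to persist for 24 hours, but the scores come at least two days apart. A programmer working from SAP 11.5.1 has to choose among at least three readings:

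- a single low score is enough;
- two successive scheduled low scores are needed, however far apart;
- the NEWS component is never met, and only discharge counts.

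These readings give different event dates for the same patient. The censoring date has the same gap, because it depends on knowing when the condition had not been met.

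Two features of the trial give this some weight. The Phase 2b stage is open label, and patients, investigators, site and CRO staff all know the treatment (Protocol 4.4), so the rule should be fixed before the data are read. Phase 2b is also meant to help choose and rank secondary endpoints for Phase 3 (Protocol 4.1), and a component without a workable definition could be kept or dropped for the wrong reason.

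**Working it through.** The documents state no power or sample size for this measure, so there is no figure to reproduce. The check compares the schedule with the definition.

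**1. Gaps between scheduled scores.** The inputs are the nominal scoring days 1 (baseline), 3, 5, 8, 11, 15 and 29 from Protocol Table 3. The gap is the later day minus the earlier day. If the score falls to 2 or less on the day after a scheduled score and stays there, the next scheduled score comes (gap − 1) days after onset.

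| Scores on days | Gap (days) | Longest delay to first low score (days) |
|---|---|---|
| 1 and 3 | 2 | 1 |
| 3 and 5 | 2 | 1 |
| 5 and 8 | 3 | 2 |
| 8 and 11 | 3 | 2 |
| 11 and 15 | 4 | 3 |
| 15 and 29 | 14 | 13 |

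No pair is one day apart. Of the 13 days from Day 2 to Day 14, four carry a score.

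**2. Visit windows.** Visits 2 and 3 may each move by 2 days, so they fall on Days 13 to 17 and 27 to 31.

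- Day 11 to Visit 2: 13 − 11 = 2 to 17 − 11 = 6 days. The longest delay rises from 3 to 5 days (onset on Day 12, scored on Day 17).
- Visit 2 to Visit 3: 27 − 17 = 10 to 31 − 13 = 18 days. The 13-day delay is therefore a nominal figure (onset on Day 16, scored on Day 29).

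**3. What the readings do to one patient.** Suppose the score falls to 2 or less on Day 4 and stays there. The first scheduled low score is on Day 5 and the next is on Day 8. A single-score reading dates the event at Day 5. A two-score reading cannot declare it before Day 8, and a strict 24-hour reading waits for discharge. With onset on Day 12, the first low score is on nominal Day 15 and the next is on Day 29.

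**4. Whether a daily score can be built.** The seven components in Appendix 16.1, matched to the daily collection:

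| Component | Daily source in hospital |
|---|---|
| Respiration rate, saturation, temperature, systolic pressure, heart rate | Vital signs, Protocol 7.3.2 |
| Supplemental oxygen | Oxygen requirement, Protocol 7.3.2 |
| Level of consciousness | Not in the protocol's daily list; among the vital signs in SAP 12.4 |

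Six of seven components are daily by the protocol, and all seven if the SAP list applies daily. Daily collection runs from Day 2 to Day 14, with Visit 2 at Day 15. After that the next data are at Day 29.

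**5. With daily scores.** The gap is 1 day. Onset on day t is confirmed on day t + 1: Day 4 on Day 5, and Day 12 on Day 13.

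**The case against.** The case for leaving the plan alone has several parts.

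- **The measure is a composite, and discharge is fully observed.** This stands. A reader might infer that the whole measure cannot be observed. The documents do not support that; only the NEWS component fails, and only when judged from the scheduled scores.
- **SAP 11.5.1 does not restrict the derivation to scheduled scores, and Protocol 7.4.5 lets components come from the hospital chart.** Both are true. However, 7.4.5 describes how to fill in a score on a scoring day and does not create scores on other days. A derivation that is possible but unwritten is still not part of the plan.
- **Two successive scheduled low scores, such as Days 3 and 5, are some evidence of a sustained fall.** They are, but they do not show what happened between them, and the SAP does not adopt that rule.
- **The measure could be said to turn into time to discharge, which SAP 11.8.2 already covers.** This is tempting but cannot be shown. The documents do not say how many patients reach a low score more than a day before leaving hospital. Nor is there ground to infer bias from the schedule itself, since the same scoring days apply to every arm.
- **Importance is limited.** The measure appears in the secondary objectives and SAP 11.5.1, but not in the secondary endpoint lists (Protocol 3.2, SAP 2.3.2). SAP 11.1 describes the pilot as exploratory. The primary endpoint, the sample size and the NEWS-by-day analysis in SAP 11.5.2 are unaffected. This stands and keeps the point below the first rank.

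**Conclusion.** The mismatch is real. As planned, the NEWS component cannot be confirmed, because the scheduled scores are nominally 2 to 14 days apart and no other rule is given. The delay in dating a first low score is up to 3 days on nominal days through Day 15, up to 5 days if Visit 2 falls at the end of its window, and about 13 days for a patient still in hospital between Day 15 and Day 29.

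These delays assume that scoring follows the schedule and that the score stays at 2 or less once it gets there. The loss of precision and the degree of overlap with time to discharge cannot be computed from the documents, so no size is put on them. The plan should be changed, because the measure has a full planned analysis and the data for a better definition are largely collected already.

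**What to change.** Amend SAP 11.5.1 as follows.

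1. Derive a daily NEWS for each hospital day from baseline to Day 15 from the daily vital signs, oxygen requirement and level of consciousness. Confirm that the eCRF captures consciousness daily, and add it if it does not.
2. Define the event as the first of two consecutive daily scores of 2 or less, or discharge if earlier. Reword the 24-hour condition, here and in the objectives, to match.
3. State which of the two days is the event date, and how the censoring date follows from it.
4. State how a missing day or a missing component is handled, including the case where Visit 2 does not fall on Day 15 and so leaves no consecutive pair.
5. State the rule for patients still in hospital after Day 15 without an event. Daily collection stops there, so daily scores cannot be derived. One option is that only discharge counts from then on.

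The cost is some programming and possibly one added daily eCRF item. If consciousness has not been recorded daily so far, programming cannot recover past days. Two daily scores also show two points in time and not continuous maintenance, which is why the wording must change with the rule. The visit schedule stays as it is.
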